5. STUDY POPULATION

Approximately 30 patients with severe pneumonia related to SARS-CoV-2 infection (COVID-19) are planned to be enrolled in this study.

5.1. Inclusion Criteria

The following inclusion criteria must be met for a patient to be eligible for inclusion in the study:

1. Age 18 to 75 years.
2. Confirmation of SARS-CoV2 infection by PCR.
3. Severe pneumonia related to SARS-CoV2 infection, defined as fever or suspected respiratory infection with radiographic abnormalities suggestive of viral pneumonia, plus at least one of the following:
 - Respiratory rate >30 breaths/min; or
 - Severe respiratory distress, as determined by the Investigator; or;
 - Oxygen saturation (SpO_2) $\leq 93\%$ on room air.
4. Female patients of childbearing potential must be willing to use adequate contraception from Screening until 30 days after the last follow-up visit. Male patients, if not infertile or surgically sterilized, must agree to use adequate contraception and not donate sperm from Day -1 until 30 days after the last follow-up visit. (Refer to [Section 7.1.6.2](#) for details regarding adequate contraception.)
5. Signed informed consent by patient or designated representative.

5.2. Exclusion Criteria

A patient who meets any of the following exclusion criteria will not be eligible for inclusion in the study:

1. Patient is intubated/mechanically ventilated.
2. In the opinion of the Investigator, patient's progression to death is imminent.
3. Treatment with immunosuppressant/immunotherapy drugs, including but not limited to IL-6 inhibitors, TNF- α inhibitors, anti-IL-1 agents and janus kinase inhibitors within 5 half-lives or 30 days (whichever is longer) prior to Day 1.
4. Use of chronic (>30 days) oral corticosteroids for a non-COVID-19-related condition in a dose higher than prednisone 10 mg or equivalent per day.
5. Weight >165 kg or <40 kg.
6. Class III or IV congestive heart failure as defined by the New York Heart Association (NYHA) or any recent onset of heart failure resulting in NYHA Class III/IV symptoms.

7. Acute coronary syndrome (eg, myocardial infarction, unstable angina pectoris) and/or any history of significant cardiovascular disease within the last 30 days. (Controlled hypertension is not a criterion for exclusion.)
8. Hospitalization for respiratory disease within 1 year before screening, or a history of chronic obstructive or restrictive respiratory disease that limits activity and requires treatment to manage symptoms, including but not limited to, severe asthma, chronic obstructive pulmonary disease (GOLD Stage 2 or higher) bronchiectasis, interstitial lung disease, pulmonary hypertension, or any other respiratory diseases requiring long-term daily oxygen therapy.
9. Renal failure requiring renal replacement therapy.
10. Patient has a chronic infection such as hepatitis B virus (HBV), hepatitis C virus (HCV), or human immunodeficiency virus (HIV), or known active tuberculosis or history of untreated tuberculosis.
11. History of anti-synthetase syndrome or known Jo-1 positivity prior to Screening.
12. Pregnancy (negative pregnancy test required for women of child-bearing potential).
13. Participation in another clinical study of an investigational agent within 3 months (small molecules), 6 months (biologics) or 5 half-lives of the agent whichever is longer.
14. Any physical examination findings and/or history of any illness that, in the opinion of the study Investigator, might confound the results of the study or pose an additional risk to the patient by their participation in the study.

5.3. Source of Patients

This will be a multi-center study. Each study center is required to obtain Institutional Review Board (IRB) and regulatory approval to conduct the study before enrollment of patients may commence. Patients meeting the study entry criteria will be eligible for enrollment.

6. STUDY CONDUCT

6.1. Patient Identification, Enrollment, and Randomization

After obtaining informed consent, patients will be screened according to the inclusion and exclusion criteria. Patients will be randomized to one of the three treatment arms based on their availability. Patients who have met all eligibility criteria will receive a unique Screening number according to the Screening order. Then, prior to dosing, each patient will be allocated a randomization number according to their chronological order of inclusion in the study. This number will correspond to a treatment (ATYR1923 or placebo) as specified on the pre-determined randomization schedule.

The master randomization schedule will be made of randomly permuted blocks of appropriate sizes, as determined by the unblinded study team member producing the schedule. The schedule will be generated electronically.

For patients who are replaced, the replacements should take the same treatment assignment as the original patient to ensure that the treatment groups stay balanced.

The randomization code will be produced within the interactive web response system (IWRS). The study center pharmacist or designated unblinded study team member will be provided access to the randomization code within the IWRS. The laboratory where the PK samples are to be analyzed will also be provided access to distinguish between samples of patients dosed with ATYR1923 versus placebo.

Patients who withdraw for any reason without completing all Screening evaluations successfully, will be considered “screen failures”. Such patients will have a limited number of electronic case report forms (eCRFs) completed.

6.2. Patient Management

All patients or their designated legal representatives must provide informed consent before the performance of any study-related procedure. Patients eligible for the study will be randomized within 24 hours before study drug administration on Day 1 and will receive a single dose of study drug (either ATYR1923 or placebo), according to their treatment assignment on a double-blind basis. Patients will have post-treatment follow-up visit assessments performed for 60 days after completion of dosing.

6.3. Patient Adherence

All patients are required to adhere to the protocol-specified dosing and visit schedules. If a patient misses a scheduled visit, attempts should be made to reschedule the visit within the visit windows specified in [Table 1](#).

6.4. Withdrawal and Replacement of Patients

6.4.1. Study Drug Discontinuation Criteria

Study drug administration must be permanently discontinued for a patient if any of the following events occur:

- A SAE that has a reasonable possibility of a causal relationship with the study drug.
- A severe IRR that includes cardiac and/or respiratory observations (see [Section 9.9](#) for Management of IRRs).
- Patient request to discontinue study drug dosing for any reason.
- Other findings that, at the discretion of the Investigator and/or Sponsor, indicate that study drug administration should be discontinued.

The Investigator has full discretion to stop study drug infusion at any time, if clinically warranted or in the patient's best interest.

All patients who have been dosed with any amount of study drug will continue to be followed for safety. Patients who discontinue study drug dosing at any time during the treatment period should return to the study center for the post treatment follow-up visits and as clinically indicated.

Patients who withdraw their consent will not receive any further study drug, but will be offered all follow-up safety assessments.

If a subject fails to attend scheduled study assessments, the Investigator must determine and document the reasons and the circumstances as completely and accurately as possible.

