4. INVESTIGATIONAL PLAN

4.1. Overall Study Design and Plan

Study ATYR1923-C-003 is a randomized, double-blind, placebo-controlled study to evaluate the safety, PD and efficacy of ATYR1923 in subjects with SARS-CoV-2 related severe pneumonia. SARS-CoV-2 infection will be confirmed using a polymerase chain reaction (PCR) based test during Screening. The Investigator, Sponsor, and patient will be blinded to treatment assignment; study center pharmacy personnel will be unblinded.

Eligible patients will be randomized 1:1:1 to a single IV dose of ATYR1923 1 mg/kg, ATYR1923 3 mg/kg, or placebo. Study drug (ATYR1923 or placebo) will be added onto institutional standard of care (SOC) for treating SARS-CoV2 infection.

A single dose of study drug will be administered on Day 1. All study drug will be administered in the hospital setting; patients who are intubated after randomization but prior to study drug administration are no longer eligible to receive study drug. As this is a single-dose study, the treatment period is 1 day. Thereafter, all patients will be followed for 60 days post-treatment. The schedule of study assessments over this period is dependent on the duration of hospitalization and whether or not the patient requires intubation.

- ***While hospitalized***, non-intubated patients will have study assessments performed on Days 2, 3, 4, 5, 6, 7, 10, and Day 14 and/or Discharge.
 - If the non-intubated patient is discharged prior to Day 14, the assessments scheduled for Day 14 and/or Discharge will be completed at the time of discharge. If discharge occurs on another scheduled study assessment day (ie, any day between Day 2 and 10), the Day 14 and/or Discharge assessments supersede that study assessment day and the patient then will proceed to outpatient telephone contact (TC) follow-up visits.
 - If a patient is discharged prior to Day 14, then outpatient TC follow-up visits are to be conducted on Day 7 (as applicable) and Day 14.

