9.2.6. Study Drug Action

For each AE, the Investigator will indicate the action taken regarding the administration of study drug per the categories in [Table 5](#).

Table 5: Study Drug Action Taken as a Result of Adverse Events

Action	Definition
Discontinued (withdrawn)	Study drug was stopped permanently due to the AE
Dosing Interrupted	Study drug regimen was modified by being temporarily halted, but drug was not stopped permanently
Dose Decreased	Study drug regimen was modified by subtraction, ie, by decreasing the strength or amount
Dose Increased	Study drug regimen was modified by addition, ie, by increasing the strength or amount
None	No change in the administration of study drug

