9.9. Management of Potential Infusion Related Reactions, Including Anaphylaxis

ATYR1923 is a biologic and as with all biologics there is a risk for IRRs. These reactions typically occur in close temporal relationship with the infusion. They may be related to cytokine release or immune mediated.

A generalized IRR could be occurring when any symptoms begin during the study drug infusion or during the post-infusion observation period. While these symptoms may be self-limiting, such symptoms may signal the possibility of a severe reaction that could escalate into a life-threatening situation.

Should a patient develop an IRR the subsequent management will depend on the nature of the IRR. Where the IRR symptoms are not cardiorespiratory in nature i.e. they comprise cutaneous rash, flushing, burning sensation etc. and are mild to moderate in intensity – the patient may complete the infusion and receive subsequent doses. The patient will need to be observed until all symptoms resolve or for 6 hours after the end of the infusion.

If the IRR symptoms constitute a cardiorespiratory risk (hypotension, dyspnea, hypoxia etc.) or any severe AE then all further dosing should be stopped for the patient. If necessary, the patient should be transferred to an acute care facility.

Vital signs, pulse oximetry, and ECGs are to be performed to gather clinical information as soon as possible after the onset of clinical symptoms of a generalized IRR (for instance, immediately after cessation of the study drug infusion if such a reaction is seen) and monitored as medically indicated. ECGs should be repeated as medically indicated.

The following tests and procedures are to be performed 1 to 2 hours after the onset of symptoms:

- ATYR1923 serum concentrations.
- Jo-1 and ADA.
- Tryptase.
- Complete safety laboratory panel, including urine analysis and urine microscopy.
- Cytokines/chemokines.

The Investigator must inform the study Medical Monitor promptly regarding any patient who experiences a generalized IRR for additional instruction.

Patients who experience generalized IRRs will continue to be monitored / have repeat assessments performed at a schedule determined by the Investigator in consultation with the Medical Monitor and Sponsor. Appropriate follow up for the patient must occur to ensure that there are no late-occurring sequelae.

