### 4.10.2 Adverse Events

Adverse events will be coded using the MedDRA Version 23.0 or higher.

Treatment-emergent AEs (TEAE) are defined as AEs that either start or worsen in severity on or after the date/time of study drug administration and through the end of study. Partial date imputation was specified in [Section 4.3](#). Imputed dates will only be used for TEAE definition.

An overall summary table of TEAEs will be provided with the number and percentage of patients (incidence) reporting an event along with the total number of events presented for the following categories:

- All TEAEs,
- TEAEs related to Study Drug,
- TEAEs by severity,
- Severity grade 3 and higher TEAEs,
- Severity grade 3 and higher TEAEs related to Study Drug,

- Serious TEAEs,
- Study drug-related serious AEs (SAEs),
- Fatal TEAEs,
- TEAEs leading to study discontinuation,
- SAEs related to COVID-19,
- TEAEs suspected as infusion-related reactions.

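### Protocol 6.4.1 and 9.9 set different triggers for stopping study drug after an infusion-related reaction, and no SAP table counts a stopped infusion

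*Protocol*

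**What the plan says.** Protocol 6.4.1 opens its list with "Study drug administration must be permanently discontinued for a patient if any of the following events occur". The bullet for infusion-related reactions (IRRs) reads "A severe IRR that includes cardiac and/or respiratory observations" and points to Section 9.9 for management. Other bullets cover a serious adverse event (SAE) with a possible causal link to study drug, the patient's own request, and other findings at the discretion of the investigator or sponsor. The section then adds "The Investigator has full discretion to stop study drug infusion at any time, if clinically warranted or in the patient's best interest". It also keeps every patient given any study drug in safety follow-up.

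Protocol 9.9 has two branches. For a reaction that is not cardiorespiratory and is mild to moderate, "the patient may complete the infusion and receive subsequent doses". Otherwise: "If the IRR symptoms constitute a cardiorespiratory risk (hypotension, dyspnea, hypoxia etc.) or any severe AE then all further dosing should be stopped".

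Protocol 4.1 states "As this is a single-dose study, the treatment period is 1 day".

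For each adverse event, Protocol 9.2.6 (Table 5) records the action taken with study drug. One category is defined as "Study drug was stopped permanently due to the AE", and another covers a temporary halt. The only discontinuation category in the tables of SAP 4.10.2 and 4.10.2.1 is "TEAEs leading to study discontinuation". SAP 4.10.1 provides exposure as a by-patient listing only.

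**The concern.** There are three linked problems.

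- **Trigger.** One section requires severity *and* cardiac or respiratory involvement. The other requires either one. The force differs too: *must* in 6.4.1, *should* in 9.9. A site that works from the 6.4.1 list alone has a narrower stopping rule than a site that works from 9.9.
- **Object.** The wording of 9.9 about later doses has nothing to refer to in a one-dose trial. In the combinations where the 6.4.1 bullet is silent, 9.9 is the only IRR-specific stopping text, and the reader must infer whether it reaches the remainder of the infusion in progress.
- **Reporting.** The primary objective is safety after one infusion. A patient whose infusion is stopped but who stays in follow-up does not enter the SAP's discontinuation row. That patient remains in the mITT and Safety Sets, which admit anyone who received any amount of drug, and no table shows how many infusions per arm were incomplete.

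At stake are consistent handling of a patient-safety rule across about 15 centers, and a by-arm description of tolerability and of dose actually received in a two-dose trial.

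**Working it through.** No power or sample-size figure bears on this point, so the check sets the texts side by side.

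**Step 1: the two triggers.** Let S mean the reaction is severe and C mean it is cardiorespiratory.

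- 6.4.1, IRR bullet: stop if S *and* C.
- 9.9: stop if C *or* S. The infusion may be completed if neither holds.

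| Reaction | 6.4.1 IRR bullet | 9.9 | Same? |
|---|---|---|---|
| Severe, cardiorespiratory | must stop | should stop | trigger yes, force no |
| Mild to moderate, cardiorespiratory | not triggered | should stop | no |
| Severe, not cardiorespiratory | not triggered | should stop | no |
| Mild to moderate, not cardiorespiratory | not triggered | may complete | yes |

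The scope differs in 2 of 4 combinations. In both, 6.4.1 is silent; it does not tell the site to continue. The difference disappears whenever the event is also a drug-related SAE, because another bullet of 6.4.1 then applies.

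**Step 2: what 9.9 tells the site to stop.** The study gives one dose (Protocol 4.1 and 7.1.1). The number of later doses is therefore 0, and the literal object of the 9.9 instruction is either empty or the rest of the current infusion. Section 9.9 mentions cessation of the infusion once, as an example of when to take vital signs and ECGs. That suggests stopping the running infusion was contemplated, but it is not stated as the rule.

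**Step 3: the SAP outputs.**

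- Overall event summary (4.10.2): 11 categories, of which 0 count a stopped or interrupted infusion.
- Summaries by system organ class and preferred term (4.10.2.1): 13, of which 0 do.
- Suspected IRRs are tabulated in both places, without regard to whether the infusion was stopped.
- A shortened infusion should be visible in the by-patient exposure listing (4.10.1) and in the disposition listing, which gives treatment duration before discontinuation (4.6.1).

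**Step 4: size of one case.** SAP 3.1.4 gives 30 patients randomized 1:1:1, so 30 / 3 = 10 per arm. One stopped infusion is 1 / 10 = 10% of an arm. If that patient stays in the study, the case adds 0 to the study-discontinuation row.

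**The case against.** The strongest defence is that a site can obey both sections in all four combinations. Section 6.4.1 is a minimum list. Its IRR bullet sends the reader to 9.9, and it gives the investigator full discretion to stop. A site that reads both would probably stop in the two disputed combinations. Some severe reactions without cardiorespiratory signs would be caught anyway: the Grade 3 description in Table 3 includes prolonged hospitalization, which overlaps the SAE criteria, so a drug-related case would trigger 6.4.1. All of this stands.

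A reader might therefore go too far in inferring that the sections give opposite orders, or that two sites are bound to handle the same reaction oppositely. The documents do not support that. It would take a site that ignores the cross-reference, or one that reads the 9.9 wording as covering later doses only.

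A reader might also infer that 9.9 is unworkable because dyspnea and hypoxia are features of the disease at entry. That is largely answered. Section 9.9 concerns symptoms that begin during the infusion or the observation period, Section 8.6.3 judges adverse events against baseline, and pre-dose SpO2 and vital signs are recorded.

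Nor would a stopped infusion be hidden. With about 30 patients, the listings should show it, suspected IRRs are tabulated, and the primary endpoint (incidence of treatment-emergent events) is fully tabulated. The documents give no IRR rate for this population, and the two possible IRRs in Protocol 2.1.1 were mild and fall where the sections agree.

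The defence does not remove the mismatch. Discretion permits stopping but does not make sites consistent, and the cross-reference leads to the sentence whose object is unclear. Listings are not by-arm counts. The sponsor itself reports events leading to study drug modification for the earlier single-dose study (Protocol 2.1.1), and this SAP has no table that would give the same figure.

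**Conclusion.** The point holds as a mismatch that needs reconciling, together with a modest reporting gap. The two sections differ in trigger and force, with different scope in 2 of 4 severity-by-type combinations. Section 9.9 carries repeat-dose wording in a one-dose trial. None of the 24 tabulated event summaries (11 + 13) counts a stopped or interrupted infusion. I would rank it below a must-fix.

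The conclusion assumes that the cardiac or respiratory observations of 6.4.1 and the cardiorespiratory risk of 9.9 mean the same thing, and that severe is used alike in both. It also assumes that the listings carry enough detail to identify a shortened infusion; the SAP does not set out the columns of the exposure listing. How often the disputed combinations would occur cannot be estimated from the documents.

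**What to change.** **Protocol.** The sponsor's medical team should reconcile 6.4.1 and 9.9 into one consistent statement that fits a single-dose study, including what it says about an infusion in progress. The clinical content is for them to decide. The cost is a wording clarification. The SAP revision history describes changes made after unblinding, so the clarification may come too late to affect dosing here. In that case the clinical study report should state how the two sections were applied.

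**SAP 4.10.2 and 4.10.2.1.** Add a row for treatment-emergent events leading to study drug discontinuation or interruption, taken from the Table 5 action field, and a count of complete and incomplete infusions by arm. The existing study-discontinuation row stays. This means extra table rows and no new data. If added after database lock, they should be labelled post hoc, as SAP 3.2 requires.

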6.4.2. Replacement of Patients

If a patient is withdrawn from the study for any reason, whether related to the study drug or not, or if a patient voluntarily withdraws before or after receiving the study drug, such patient will be considered an early-termination patient.

Investigator will make every effort to ensure that early-termination patients who have received study drug complete the safety follow up assessments.

Patients who are randomized and do not receive study drug will be replaced at the Sponsor's discretion. The decision regarding the replacement of patients will be documented.

6.4.3. Study Withdrawal Criteria

Patients will be informed that they have the right to discontinue from the study and withdraw consent at any time for any reason, without prejudice to their medical care. The Investigator also has the right to withdraw patients from the study for any of the following reasons:

- Patient non-adherence to study drug or protocol requirements.
- Patient unwillingness to continue in the study.
- Any other reason, based upon the medical judgment of the Investigator.

The reason for study withdrawal is to be documented in the patient's source documents and electronic case report form (eCRF).

At the time of discontinuation from the study, patients are to have all the assessments planned for the final follow-up visit performed after the last study drug dose, if feasible.

6.5. Study Completion

A patient is considered to have completed the study if they completed all dosing and all follow-up visits.

